Sponsor/Development Innovations Study Numbers: AC699-001/BRE 401

Final Protocol: 07 May 2024 Version 4.0

^a For a patient to be considered "evaluable," he or she must have met the minimum safety evaluation requirements of the study, and/or experienced a DLT.

- Grade 3 non-hematologic laboratory abnormalities, other than liver function tests, will not be considered a DLT unless they are associated with clinical manifestations which lead to medical intervention and/or hospitalization
- Potential drug-induced livery injury consistent with Hy's Law (Appendix E),
 defined as AST and/or ALT > 3 × ULN with concurrent total bilirubin > 2 × ULN
 without findings of cholestasis (alkaline phosphatase [ALP] >2 × ULN)
- Grade 3 or higher electrolyte abnormality that lasts > 72 hours, unless the patient
 has clinical symptoms, in which case all Grade 3 or higher electrolyte abnormality
 regardless of duration should count as a DLT

Determination of Dose-Limiting Toxicities

The patient population used for determination of DLTs will consist of patients who have met the minimum safety evaluation requirements of the study, and/or who have experienced a DLT. Minimum safety evaluation requirements will be met if, during Cycle 1 of treatment, the patient receives at least 75% of planned total doses of AC699, completes all required safety evaluations, and is observed for at least 28 days following the first dose of AC699. Patients who have experienced a DLT may be allowed to continue treatment at a lowered dose, if in the opinion of the Investigator, Medical Monitor, and Sponsor, they continue to derive benefit.

Patients who discontinue treatment early due to disease progression or withdrawal will be asked to have all EOT safety evaluations performed as described in the protocol (see Section 7.6). If a patient withdraws from treatment during Cycle 1 due to any reason other than DLT and does not meet the minimum requirements for DLT assessment, that patient will be replaced.

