6.2.1 Specific Recommendations for Liver Function Test Abnormalities

For patients with Grade 3 liver enzyme elevations (AST/ALT), AC699 should be held until the values recover to \leq Grade 1 or baseline. Patients with an elevation of AST/ALT \geq 3 × ULN in conjunction with a bilirubin \geq 2 × ULN may remain in the study if a correctable, non-drug related cause of the liver test evaluations can be documented; otherwise, the patient must be discontinued from the study.

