When a subject meets any of the identification criteria, in isolation or in combination, the central laboratory, if applicable, will immediately send an alert to the Investigator.

Where the identification criteria are met in samples analyzed by a local laboratory, the Investigator will:

- Notify the Sponsor's representative
- Request a repeat of the test (new blood draw) by the local laboratory
- Complete the appropriate unscheduled laboratory electronic case report form (eCRF) module(s) and the original laboratory test eCRF

When the identification criteria are met from central or local laboratory results the Investigator will without delay determine whether the subject meets PHL criteria (see "Definitions") by reviewing laboratory reports from all previous visits (including both central and local laboratory results).

The Investigator will without delay review each new laboratory report and if the identification criteria are met will:

- Notify the Sponsor's representative
- Determine whether the subject meets PHL criteria (see "Definitions") by reviewing laboratory reports from all previous visits
- Promptly enter the laboratory data into the laboratory eCRF

Follow-up

Potential Hy's Law criteria not met

If the subject does not meet PHL criteria the Investigator will:

- Inform the Sponsor's representative that the subject has not met PHL criteria
- Perform follow-up on subsequent laboratory results according to the guidance provided in the clinical study protocol

Potential Hy's Law criteria met

If the subject does meet PHL criteria the Investigator will:

- Determine whether PHL criteria were met at any study visit prior to starting study treatment (see Section 11 Safety Reporting)
- Notify the Sponsor's representative that the subject has met PHL criteria

The Investigator contacts the Medical Monitor, to provide guidance, discuss, and agree an approach for the study subjects' follow-up and the continuous review of data. Subsequent to this contact the Investigator will:

- Monitor the subject until liver biochemistry parameters and appropriate clinical symptoms and signs return to normal or baseline levels, or as long as medically indicated
- Investigate the etiology of the event and perform diagnostic investigations as discussed with the Medical Monitor.
- Complete the liver eCRF modules as information becomes available

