- If at any time (in consultation with the Medical Monitor) the PHL case meets serious criteria, report it as an SAE using standard reporting procedures.

CONFIDENTIAL

Sponsor/Development Innovations Study Numbers: AC699-001/BRE 401

Final Protocol: 07 May 2024 Version 4.0

Review and assessment of potential Hy's Law cases

The instructions in this section should be followed for all cases where PHL criteria are met.

No later than 3 weeks after the biochemistry abnormality was initially detected, the Investigator contacts the Medical Monitor in order to review available data and agree on whether there is an alternative explanation for meeting PHL criteria other than DILI caused by the investigational product. The Accutar Biotechnology, Inc. Clinical Lead or equivalent and Medical Monitor will also be involved in this review together with other subject-matter experts as appropriate.

According to the outcome of the review and assessment, the Investigator will follow the instructions below.

If there is an agreed alternative explanation for the ALT or AST and TBL elevations, a determination of whether the alternative explanation is an AE will be made and subsequently whether the AE meets the criteria for a SAE:

- If the alternative explanation is not an AE, record the alternative explanation on the appropriate eCRF.
- If the alternative explanation is an AE/SAE, record the AE/SAE in the eCRF accordingly and follow the reporting standard practices.

If it is agreed that there is no explanation that would explain the ALT or AST and TBL elevations other than the investigational product:

Report an SAE (report term Hy's Law) according to the Sponsor's standard processes.

- The 'Medically Important' serious criterion should be used if no other serious criteria apply.
- As there is no alternative explanation for the HL case, a causality assessment of 'related' should be assigned.

If there is an unavoidable delay of over 3 weeks in obtaining the information necessary to assess whether or not the case meets the criteria for HL, then it is assumed that there is no alternative explanation until such time as an informed decision can be made:

- Report an SAE (report term Potential Hy's Law) applying serious criteria and causality assessment as per above.
- Continue follow-up and review according to the agreed plan. Once the necessary
 supplementary information is obtained, repeat the review and assessment to determine

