 whether HL criteria are met. Update the SAE report according to the outcome of the
 review amending the reported term if an alternative explanation for the liver biochemistry
 elevations is determined.

Actions required when potential Hy's Law criteria are met before and after starting study treatment

This section is applicable to subjects with liver metastases who meet PHL criteria on study treatment having previously met PHL criteria at a study visit prior to starting study treatment.

At the first on-study treatment occurrence of PHL criteria being met, the Investigator will determine if there has been a significant change in the subjects' condition compared with the last visit where PHL criteria were met.

CONFIDENTIAL

Sponsor/Development Innovations Study Numbers: AC699-001/BRE 401

Final Protocol: 07 May 2024 Version 4.0

- If there is no significant change, no action is required.
- If there is a significant change, notify the Sponsor's representative.

A "significant" change in the subject's condition refers to a clinically relevant change in any of the individual liver biochemistry parameters (ALT, AST, or TBL) in isolation or in combination, or a clinically relevant change in associated symptoms. The determination of whether there has been a significant change will be at the discretion of the Investigator, this may be in consultation with the Medical Monitor if there is any uncertainty.

Actions required for repeat episodes of potential Hy's Law

This section is applicable when a subject meets PHL criteria on study treatment, and has already met PHL criteria at a previous on-study treatment visit.

The requirement to conduct follow-up, review, and assessment of a repeat occurrence(s) of PHL is based on the nature of the alternative cause identified for the previous occurrence.

The Investigator should determine the cause for the previous occurrence of PHL criteria being met and answer the following question:

Was the alternative cause for the previous occurrence of PHL criteria being met found to be the disease under study (e.g., chronic or progressing malignant disease, severe infection, or liver disease), or did the subject meet PHL criteria prior to starting study treatment and at first onstudy treatment visit, as described in "Actions required when potential Hy's Law criteria are met before and after starting study treatment".

- If No: Follow the process described in "Potential Hy's Law criteria not met".

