- If Yes: Determine if there has been a significant change in the subject's condition compared with when PHL criteria were previously met.

If there is no significant change, no action is required.

If there is a significant change, follow the process described in "Follow-up".

A "significant" change in the subject's condition refers to a clinically relevant change in any of the individual liver biochemistry parameters (ALT, AST, or TBL) in isolation or in combination, or a clinically relevant change in associated symptoms. The determination of whether there has been a significant change will be at the discretion of the Investigator; this may be in consultation with the Medical Monitor if there is any uncertainty.

CONFIDENTIAL

Sponsor/Development Innovations Study Numbers: AC699-001/BRE 401

Final Protocol: 07 May 2024 Version 4.0

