(both high and low), the shift in both directions will be presented. For parameters that cannot be graded per CTCAE, shift tables based on the normal ranges will be presented for both the minimum and maximum values within 30 days post-treatment. Normal lab ranges will be based on local lab ranges.

A listing of potential Hy's Law cases will be provided (defined as alanine or aspartate aminotransferase $> 3 \times$ upper limit of normal with concurrent total bilirubin $> 2 \times$ upper limit of normal without findings of cholestasis [alkaline phosphatase $< 2 \times$ upper limit of normal]).

All lab data will be provided in listings. Urinalysis will not be summarized and only listed.

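### Appendix E sends some repeat potential Hy's Law cases to the criteria-not-met steps, and the SAP's potential Hy's Law listing omits cases the protocol counts

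*Protocol*

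**What the plan says.** **Repeat episodes.** In Appendix E, the section on repeat episodes of potential Hy's Law (PHL) states its scope: "This section is applicable when a subject meets PHL criteria on study treatment, and has already met PHL criteria" at an earlier on-treatment visit. It asks whether the earlier episode was attributed to the disease under study, or whether the patient met PHL both before treatment and at the first on-treatment visit.

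- Answer no: "If No: Follow the process described in" the block *Potential Hy's Law criteria not met*. That block has two steps. The site tells the Sponsor's representative "that the subject has not met PHL criteria", and it follows later laboratory results in the ordinary way.
- Answer yes, without a significant change: nothing further is required.
- Answer yes, with a change: "If there is a significant change, follow the process described in" *Follow-up*.

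The Appendix E section on review and assessment of PHL cases says: "The instructions in this section should be followed for all cases where PHL criteria are met". Section 6.2.1 adds that a patient with AST or ALT ≥3× the upper limit of normal (ULN) and bilirubin ≥2× ULN "may remain in the study if a correctable, non-drug related cause of the liver test evaluations can be documented", and otherwise must be discontinued.

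**Case definition.** Appendix E defines PHL as AST or ALT ≥3× ULN with total bilirubin (TBL) ≥2× ULN. Alkaline phosphatase (ALP) plays no part. The transaminase rise must come first or on the same day, with no limit on the interval. SAP 6.4 promises a listing of potential Hy's Law cases defined by AST or ALT >3×, concurrent TBL >2× "upper limit of normal without findings of cholestasis", the last meaning ALP <2× ULN. This is close to the dose-limiting toxicity (DLT) criterion in Protocol 5.1, which has the same strict cut-offs "without findings of cholestasis (alkaline phosphatase [ALP] >2 × ULN").

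**The concern.** The repeat-episode section covers only patients who meet PHL criteria, so a branch inside it that ends in a statement that the criteria were not met is false for everyone who reaches it. It also conflicts with the rule that all PHL cases are reviewed. At stake is a second liver signal in a patient who has continued on a first-in-human drug. A second episode is also a test of whether the first was correctly attributed.

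For the listing, the SAP uses a term that the protocol defines, but applies a narrower test. A reader would take the listing as the complete set of PHL cases, and it would not be. Raised ALP is foreseeable here: the inclusion criteria admit liver metastases and lytic bone lesions and set no ALP ceiling. Under Appendix E, raised ALP is weighed when deciding whether a PHL case is Hy's Law. The SAP filter removes such cases before that judgement is displayed. SAP section 8 declares no change from the protocol.

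**Working it through.** **(a) Tracing the branch.** No arithmetic applies, so the destinations are set side by side.

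| Repeat PHL case | Destination in Appendix E | What the site does there |
|---|---|---|
| Earlier episode attributed to disease, no significant change | None | Nothing further |
| Earlier episode attributed to disease, significant change | *Follow-up* | PHL cases: Medical Monitor contact, monitoring to resolution, etiology work-up, liver eCRF modules, SAE report if serious |
| Earlier episode not attributed to disease, and PHL not met both before treatment and at the first on-treatment visit | *Potential Hy's Law criteria not met* | Reports that criteria were not met; ordinary laboratory follow-up |

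The third row gets none of the work-up in the second, however much the liver values have changed. Section 6.2.1 limits who can be in that row. A patient whose first episode had no documented correctable, non-drug cause should already be off the study. Those left are mainly patients whose first episode had such a cause and whose cause was not the disease. The group is narrow but not empty.

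**(b) Comparing the definitions.** Inputs, as multiples of ULN:

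- PHL (Appendix E): transaminase ≥3 and TBL ≥2, any ALP, any interval.
- SAP 6.4: transaminase >3 and TBL >2 and ALP <2, concurrent. The SAP does not define concurrent; same day is assumed.
- DLT laboratory criterion (Protocol 5.1): transaminase >3 and TBL >2, concurrent, and ALP not >2.

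For on-treatment values, every SAP case is a PHL case: >3 implies ≥3, >2 implies ≥2, and same-day rises satisfy the ordering rule. The converse fails:

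| ALT, TBL, ALP (× ULN) | PHL | SAP listing | DLT laboratory criterion |
|---|---|---|---|
| 5, 3, 2.5, same day | yes | no | no |
| 5, 3, 1.0, TBL rise 7 days later | yes | no | no |
| 5, 3, 2.0, same day | yes | no | yes |
| 3.0, 2.0, 1.0, same day | yes | no | no |
| 5, 3, 1.0, same day | yes | yes | yes |

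The first two rows carry the point; the third and fourth turn on exact ties.

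A grid confirms that each difference drops cases on its own. It crosses transaminase 2.9, 3.0, 3.1, 5, 8; TBL 1.9, 2.0, 2.1, 4; ALP 1.0, 1.9, 2.0, 2.1, 4; and TBL lag 0, 1, 7, 21 days.

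- PHL: 4 × 3 × 5 × 4 = 240 combinations.
- SAP listing: 3 × 2 × 2 × 1 = 12, all of them PHL.
- Dropped by ALP alone: 3 × 2 × 3 × 1 = 18.
- Dropped by timing alone: 3 × 2 × 2 × 3 = 36.
- Dropped by an exact threshold alone: (4 × 3 − 3 × 2) × 2 × 1 = 12.

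These counts depend on the chosen grid. They show direction and say nothing about how often patients would be missed.

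**The case against.** **On (a).** Appendix E has safeguards before the branch. Any report meeting the identification criteria obliges the Investigator to notify the Sponsor's representative, determine PHL status and enter the data promptly, and a local-laboratory result also needs a repeat draw. Section 6.2.1 is not limited to first episodes, so a repeat again requires a documented cause or discontinuation, and SAE reporting still applies. The criteria-not-met block also opens on a condition that a repeat PHL case cannot satisfy, so a careful site would probably query it. And a disease-attributed repeat without significant change gets even less than the no branch.

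All of this stands, and it makes silent loss of a case unlikely. It does not make the instruction correct. The general review rule does not settle the conflict either, because the repeat-episode section says that the need for follow-up and review depends on the cause of the previous episode. A site could reasonably treat that section as controlling.

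**On (b).** The SAP wording follows a criterion in the protocol body, so this is partly a matter of labelling. Exact ties have little practical weight, and Appendix E's own identification list prints >3× for AST and ALT. Omitted patients remain visible in the laboratory listings, shift tables, discontinuation listings and the liver-assessment listing of SAP 6.9. No estimate or dose decision is tied to the SAP 6.4 listing.

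This also stands, and it makes (b) the lesser point. The ALP and timing gaps remain without any tie. At ALP exactly 2.0× the SAP departs even from the DLT wording it resembles. Also, the liver eCRF modules are required only under the criteria-met steps, so a repeat case sent down the no branch may lack them.

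**Conclusion.** Both parts hold and should be fixed. In (a), the protocol gives a false instruction for a defined, narrow group and contradicts its own rule on reviewing PHL cases. In (b), the listing is a strict subset of the on-treatment PHL cases its label names; a patient discontinued under Section 6.2.1 can be absent from it. The size in patients is unknown because the documents give no rate of PHL, repeat PHL or raised ALP in this population. No data are lost and no endpoint estimate changes. The conclusion on timing assumes that concurrent in the SAP means the same day; the conclusion on ALP needs no such assumption.

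**What to change.** **Protocol Appendix E, repeat episodes.** Change the destination of the no branch to *Potential Hy's Law criteria met*, followed by *Review and assessment of potential Hy's Law cases*.

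**SAP 6.4.** Define the listing by the Appendix E rule: AST or ALT ≥3× ULN with TBL ≥2× ULN on or after the transaminase rise, after first dose, any ALP, any interval. Show ALP and baseline liver values as columns; baseline matters because eligibility allows AST and ALT up to 5× ULN with liver metastases, and bilirubin up to 5× ULN in Gilbert's syndrome. Flag the subset meeting the DLT laboratory criterion, with cholestasis taken as ALP >2× ULN as in Protocol 5.1.

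**Cost.** One cross-reference in the protocol and one listing specification in the SAP. No new tests, visits or data.

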Appendix F: PK Sampling Timepoints

	Timepoints relative to AC699 dosing	ECG (in triplicate)
	Pre-dose	X
	1 hour (± 5 min)	X
	2 hour (± 5 min)	X
Cycle 1 Day 1 and 15	4 hour (± 5 min)	X
	6 hour (± 10 min)	X
	8 hour (± 10 min)	
	24 hour (± 1 hour)	
Cycle 2 Day 1	Pre-dose	X
Cycle 3 Day 1	Pre-dose	X
Cycle 4 Day 1	Pre-dose	X
Cycle 6 Day 1	Pre-dose	X

Additional unscheduled PK samples may be drawn during the study for safety reasons. Should a patient require a dose change, additional PK samples to ensure safety and efficacy parameters, may be required. These PK samples will be collected at the first cycle following the dosing change, and at the same time points as Cycle 1 Day 1 and Cycle 1 Day 15. Subsequent pre-dose PK samples may be requested at the next 3 cycles following the dosing change. Decisions as to whether or not these samples are to be collected will be determined in consultation with the Medical Monitor.

Final Protocol: 07 May 2024 Version 4.0

Appendix G: Clinical Protocol Amendment AC699-001/BRE 401 Summary of Changes

VERSION NUMBER: 4.0 **VERSION DATE:** 07 May 2024

Additions to the text are **bolded**, and deletions from the text are crossed off. Only the parts of sections with changes are presented. Please note that formatting changes and minor changes to punctuation, spelling, and abbreviations that do not affect meaning are not noted in this summary.

Global changes made throughout the protocol include:

- Increase in the approximate number of patients to **100** from 80 to be enrolled.
- Schedule of Assessments

The Schedule of Assessments (SOA) table was updated to reflect the changes made in the body of the protocol. Footnotes b, h, l and m were revised.

Two new lines were added in the SOA. One line for **Concomitant Medication Log** and one line for **Serum Pregnancy Test (WOCBP, pre- or perimenopausal)**

• Inclusion criteria modified as follows:

Criterion #3 defines 2 parts where upon female participants much meet one of the described criteria in Part a) or Part b). Part a) was added while Part b) already existed.

a) Premenopausal or perimenopausal women must receive concurrent treatment with a luteinizing hormone-releasing hormone (LHRH) agonist beginning at least 4 weeks before the start of trial therapy and agree to continue the LHRH agonist throughout the duration of study treatment, have a negative serum pregnancy test within 7 days of initiating treatment, and agree to follow guidelines for use of highly effective contraception as outlined in Appendix C during the study and for 90 days following the last dose of study drug.

Criterion #11 Liver function updated as follows:

• Total bilirubin ≤1.5 × ULN (≤5 × ULN for patients with known Gilbert's syndrome)

Criterion #15 New inclusion criteria added for backfill patients. Additional backfill patients must have historical testing to confirm ESR1 mutations and must meet all inclusion criteria listed here.

• Exclusion criteria modified as follows:

Criterion #5 Exclusion criteria modified to expand the windows in 2 of the criteria. Any of the following cardiac criteria currently or within the last 6 months.

CONFIDENTIAL

Sponsor/Development Innovations Study Numbers: AC699-001/BRE 401

Final Protocol: 07 May 2024 Version 4.0

- mean resting corrected QT interval (QTcF) >470 msec within 28 days prior to the first administration of study drug.
- patients with a left ventricular ejection fraction (LVEF) <50% or the lower limit of normal of the institutional standard within 28 days prior to the first administration of study drug.

Section 5.1 Treatment Plan

- Concomitant medications will be recorded by the patients during Cycle 1 Days 1-15 as described in the SOA and Section 5.1:
 - In addition, patients will be required to record all concomitant medications taken during Cycle 1 Days 1 through 15 on a Concomitant Medication Log. A copy of the concomitant medication log is provided in the study reference materials.
- Backfill patients are described in Section 5.1 Treatment Plan and new Stopping Rules were added.
 - Only the additional backfill patient must have historical documentation of an ESR1 mutation from a tissue sample or blood sample. This does not apply to initial dose-escalation cohorts.
- Stopping rules

A cumulative incidence of any of the following treatment-related events will trigger a hold on further patient enrollment for all dose cohorts until the SRC determines if it is safe to continue:

- Grade 4 adverse events (AEs) > 25%,
- Serious adverse events (SAEs) > 25%,
- AEs leading to discontinuation from study > 25%,
- Grade 5 AEs > 10%.
- The patient dosing diary was updated. The patient will be required to record the exact time of AC699 dosing during the study and the time of dosing of other concomitant medications during Cycle 1 Day 1 through Cycle 1 Day 15.
- Appendix C: Guidelines for Women of Childbearing Potential and Fertile Male Patients was **updated.**

Section 7.2 Screening

Study Drug: AC699

Review patient menopausal status. Premenopausal or perimenopausal women must receive concurrent treatment with an LHRH agonist and agree to use highly effective contraception as defined in Appendix C. Draw estradiol and FSH levels for participants who do not meet other definitions of postmenopausal as defined in the inclusion criteria, if indicated.

CONFIDENTIAL

Sponsor/Development Innovations Study Numbers: AC699-001/BRE 401

Section 7.3.3. Biomarkers (circulating tumor [ctDNA] and circulating tumor cells [CTC] - Assessments Ever 2 Cycles

Patients will be evaluated with ctDNA assessments at the pre-dose visit, on Day 1 of Cycle 1 and Cycle 2, and at the EOT visit.

CTC assessments **will be evaluated** at pre-dose, on Day 1 of Cycle 1 and Cycle 2, and on Day 1 of all even numbered cycles thereafter. The **CTC** assessments should also be collected at the EOT visit.

Section 8.1.2 Preparation and Administration of AC699

[figure not shown]
The following will be recorded in the dosing diary: exact time of AC699 dosing during the study, and the time of dosing of concomitant medications in a Concomitant Medication Log during the first cycle from Cycle 1 Day 1 through Day 15.

Final Protocol: 07 May 2024 Version 4.0

Additions to the text are **bolded**, and deletions from the text are crossed off. Only the parts of sections with changes are presented. Please note that formatting changes and minor changes to punctuation, spelling, and abbreviations that do not affect meaning are not noted in this summary.

Changes in Study Chair Address, Medical Monitor and Address, and Sponsor Representative

On Pages 1, 3 and 5 updates have been made to the contact information and names of the key leaders for the study. [name], Study Chair has had an address change, the previous Medical Monitor, [name] has been replaced by [name] and the Sponsor Representative [name] has been replaced by [name]. The updated contacts are:

Synopsis, Number of Patients, Study Design, Statistical Design, and wherever patient enrollment is described in the protocol.

This study is a Phase I, first-in-human, open-label dose-escalation study of AC699 given as a single agent. Pending the totality of data, including but not limited to safety and pharmacokinetics, selected dose level(s) may be expanded to approximately **20** 15 patients (per dose level) to further support the evaluation of the Objectives set hereabove. Approximately **80** 60 patients may be enrolled in this study.

CONFIDENTIAL

Sponsor/Development Innovations Study Numbers: AC699-001/BRE 401

Final Protocol: 07 May 2024 Version 4.0

Synopsis, Section 3.1 Inclusion Criteria

- 3. Female patients only: must be post-menopausal as defined by:
 - 6 months of spontaneous amenorrhea with serum follicle-stimulating (FSH) levels >40 mIU/ml and an estradiol value in the post-menopausal range per institutional standards <40 pg/mL (140 pmol/L),

Synopsis and Section 3.2 Exclusion Criteria

- 5. Any of the following cardiac criteria currently or within the last 6 months:
 - Any factors that increase the risk of QTc prolongation or risk of arrhythmic events such as heart failure, **acute** hypokalemia, congenital long QT syndrome, family history of long QT syndrome or unexplained sudden death under 40 years-of-age, or any **new** concomitant medication known to prolong the QT interval
- 6. As judged by the Investigator, any evidence of severe or uncontrolled systemic diseases, including uncontrolled hypertension, uncontrolled diabetes mellitus, active bleeding diathese, and any serious active infection requiring systemic treatments. Screening for chronic conditions is not required.

Schedule of Assessments Flow Chart

Footnote C added: total CO₂ and creatinine kinase [if CK is elevated, and elevation is clinically significant in the judgment of the Investigator, then CK-MB, troponin I, and myoglobin should be reactively tested, with further follow-up as clinically warranted]

Footnote h modified: Menopausal status of all female patients <**60 years** old should be confirmed unless there is documentation that the patient is post-menopausal for 12 months or longer, **or a history of a bilateral oophorectomy.** This will include measurement of blood estradiol and follicle stimulating hormone (FSH) **levels in the post-menopausal range per institutional standards.**

Footnote l: Blood samples for ctDNA (next generation sequencing) and CTCs will be collected **pre-dose on Day 1 of Cycle 1 and Cycle 2, and on Day 1 of all even numbered cycles thereafter, and at the EOT visit.** Optional paired tumor biopsies will be collected at screening and within 5 days following Cycle 2 Day 1 as outlined in Section 7.8.1.1.

